3.2.4 Glycemic Control Monitoring

Subjects with hyperglycemia based on blood glucose levels during the treatment period may receive approved anti-diabetic medication. In addition, adjustment by the investigator to the pre-screening anti-diabetic therapies will be recommended if hypoglycemia occurs.

PLACEBO RUN-IN PERIOD

During the placebo run-in period subjects will be instructed to determine the SMBG daily after fasting overnight for a minimum of 8 h. If the fasting blood glucose is ≥ 250 mg/dL (13.9 mmol/L) the subject should contact the clinic and the investigator will determine whether the participant should attempt to improve diet and exercise to maintain glycemic control or if the participant must discontinue from the study and initiate a more intense pharmacological regimen for glucose control. Subjects with SMBG readings ≥ 250 mg/dL (13.9 mmol/L) and severe clinical signs or symptoms of hyperglycemia during the screening or run-in periods, including weight loss, blurred vision, increased thirst, increased urination, or fatigue should be excluded. Patients with symptomatic hypoglycemia should be withdrawn from the study if symptoms are severe.

MAIN TREATMENT PERIOD

During the main treatment period subjects will be advised to continue daily fasting SMBG measurements. Intensification of the anti-diabetic regimen should adhere to the guidelines described in [Section 5.2.4](#) for “*Prescription of Rescue Medication*”.

Study subjects should contact the clinic if any fasting SMBG is ≥ 270 mg/dL (15 mmol/L) from week 1 to week 6, ≥ 240 mg/dL (13.3 mmol/L) between week 6 and week 12, or ≥ 200 mg/dL (11.1 mmol/L) between week 12 and week 24. Blood glucose values collected via SMBG will be reviewed at study visits by the investigator. In addition, hyperglycemia will be monitored by fasting plasma glucose (FPG) at each clinical visit except visit V2.

If hyperglycemia is identified through SMBG or FPG measurements, the investigator will determine whether the subject had fasted for a minimum of 8 hours prior to the morning blood draw to ensure that the glucose value is truly from a fasting sample. If proper fasting had not occurred, the subject will be asked to return for a repeat blood test within a week.

If a concomitant medication for hyperglycemia is to be prescribed, a sample must be drawn prior to the administration of the rescue medication so that an HbA1c value can be assessed. Starting metformin in patients with an eGFR between 30-45 mL/minute/1.73 m² is not

recommended. The investigator should assess the benefits and risks of continuing metformin treatment for patients who have been taking metformin and whose eGFR falls below 45 mL/minute/1.73 m². Metformin therapy should be discontinued if the patient's eGFR falls below 30 mL/minute/1.73 m².

Subjects will be instructed to contact the clinic staff for hypoglycemia, defined as: 1) any SMBG value < 70 mg/dL (3.9 mmol/L); or 2) any symptoms of hypoglycemia that resolve with food intake, with or without an accompanying SMBG value. Hypoglycemia may also be detected by FPG values, measured by central laboratory at every clinic visit, except V2, using the same criteria as for SMBG values.

If recurring hypoglycemia (*i.e.*, clinically significant hypoglycemia occurring on multiple different days) is identified during the main treatment period, the dose and frequency of background (pre-screening) medical therapy for diabetes should be reduced at the discretion of the investigator. If the subject is taking insulin and OHA, the dose of insulin should be reduced first, and, if necessary to prevent further hypoglycemia, insulin should be discontinued before oral hypoglycemic agents are reduced. If the subject is taking only OHAs or GLP-1 agonist, the dose or frequency of these background medications can be reduced at the discretion of the investigator.

3.2.5 OTHER SAFETY MONITORING ACTIVITIES

During the course of the study investigators will manage blood pressure and lipid values according to accepted standards of care for the management of hypertension and dyslipidemia.

3.2.5.1 Renal Function

Evaluation and management of subjects with and at risk for acute kidney injury (AKI) should be performed during the study period based on the Kidney Disease: Improving Global Outcomes (KDIGO) Clinical Practice Guideline in 2012 ([KDIGO Clinical Practice Guideline for AKI, 2012](#)). The classification/staging System for AKI is described in [Appendix 3](#).

If serum creatinine increases suggesting a possible stage 1 AKI, the investigator should confirm the increase in serum creatinine within 48 h of learning the result and enter an AE into the CRF if the serum creatinine does not spontaneously returns to < 0.3 mg/dL from baseline. The investigator should encourage the subjects to maintain hydration and pursue any additional clinically relevant investigations to elucidate the cause or potential consequences of the decline in renal function. Study drug administration may be suspended if clinically indicated until the creatinine value returns to < 0.3 mg/dL from baseline. Serum creatinine should be monitored based on the investigator's judgment until creatinine returns to baseline level, within 0.3 mg/dL difference.

If serum creatinine increases or other signs suggesting a possible stage 2 or 3 AKI, the subject should be monitored daily and nephrology consultation or hospitalization within 24 h should be considered. Study drug administration should be stopped until the creatinine value returns to < 0.3 mg/dL from baseline. If potentially life-threatening conditions (*i.e.*, uremia,

pulmonary edema, arrhythmia, disseminated intravascular coagulation, hyperkalemia, metabolic acidosis) are present occurring in the setting of a possible stage 2 or 3 AKI event, the administration of study drug must be stopped and the medical monitor should be informed. The medical monitor will advise on whether the study drug can be restarted after the resolution of the potentially life-threatening condition. Local laboratory testing will be acceptable when immediate lab results are necessary for clinical assessment.

If interrupted, study drug may be reinitiated when serum creatinine returns to within 0.3 mg/dL of the randomization value or if renal function remains 0.5 mg/dL above the randomization value but an alternative cause of the worsened renal function has been identified. Dosing of study drug will be permanently discontinued if the subject is to start dialysis or other renal replacement therapies.

The renal function monitoring plan is summarized in Figure 1.

[figure not shown]

Figure 1. Renal Function Monitoring Plan

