6.16.2 Eliciting and Reporting AEs

The investigator will periodically assess subjects for the occurrence of AEs after a subject consents to participation in the study. To avoid bias in collecting information about AEs, the investigator should ask subjects the following question: "How have you felt since you were last checked?" All AEs (serious and non-serious) reported by the subject must be recorded on the source documents and CRFs provided by the sponsor.

It is the investigators responsibility to review the results of all laboratory tests as they become available. For each abnormal laboratory test result the investigator needs to ascertain if this is a clinically significant change from baseline for that individual subject (this determination, however, does not necessarily need to be made the first time an abnormal value is observed. The investigator may repeat the laboratory test or request additional tests to verify the results of the original laboratory tests). If the laboratory value is determined to be a clinically significant and abnormal change from baseline for that subject, this is considered a laboratory AE.

Hypoglycemia is defined as any FPG or SMBG value <70 mg/dL and documented as described in [Section 6.16.11](#).

Any increase in liver function tests (AST, ALT, or bilirubin) greater than 3 times the ULN for the laboratory utilized will be considered a laboratory AE.

In addition, the sponsors Medical Monitor or its designated personnel must be notified immediately by telephone, email, or fax of any immediately reportable AEs (IRAE) according to the procedure outlined below. Special attention should be paid to recording hospitalization and concomitant medications.

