6.16.14 Renal failure events

Renal function and potential AKI will be monitored closely as described in [Section 3.2.5.1](#). Events potentially representing renal failure events, including reversible and irreversible AKI, oliguria, and use of renal replacement therapy, etc. should be evaluated with documentation of signs, symptoms, laboratory results, and treatment.

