Appendix 3 KDOQI Chronic Kidney Disease Classification and Acute Kidney Injury Stage Definition

Chronic kidney disease (CKD) is defined as either kidney damage or GFR < 60 mL/min/1.73 m³ for ≥3 months. Kidney damage is defined as pathologic abnormalities or markers of damage, including abnormalities in blood or urine tests or imaging studies ([NFK KDOQ guidelines](#)).

Stages of CKD are outlined in Table 2.

Table 2. KDOQI CKD Stages

Stage	Description	GFR (mL/min/1.73 m ²)
1	Kidney damage with normal or ↑↓GFR	≥ 90
2	Kidney damage with mild ↓GFR	60-89
3	Moderate ↓GFR	30-59
4	Severe ↓GFR	15-29
5	Kidney failure	< 15 (or dialysis)

Acute kidney injury stages based on the Definition by the Acute Kidney Injury Network (AKIN) are outlined in Table 3 ([KDIGO Clinical Practice Guideline for AKI, 2012](#)).

Table 3. Classification/Staging System for Acute Kidney Injury

Stage	Serum creatinine criteria	Urine output criteria
1	1.5 to 1.9 times baseline or ≥ 0.3 mg/dL (≥ 26.5 μmol/L) increase from baseline	<0.5 mL/kg/h for 6 to 12 h
2	2.0 to 2.9 times baseline	< 0.5 mL/kg/h for ≥ 12 h
3	3.0 times baseline, or Increase in serum creatinine to ≥4.0 mg/dL (≥ 353.6 μmol/L), or Initiation of renal replacement therapy, or In patients < 18 years, decrease in eGFR to < 35 mL/min per 1.73 m ²	< 0.3 mL/kg/h for ≥ 24 h or anuria for ≥ 12 h

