9.3.3. AE of Special Interest

AE of special interest include UTI, GMI, diuretic effects, hepatotoxicity, MACE, hypoglycemia, fracture, malignancy, hypersensitivity reactions, hypotensive episodes, acid base disorders, DKA, renal failure events, and amputations. The AEs of special interest, except for MACE and amputations, will be prospectively identified based on the MedDRA PTs in the AEs log by a medical expert prior to the data base lock and unblinding of the individual subject treatment assignment. The list of AEs of special interest will be confirmed in a peer review process. Adjudicated MACE will be summarized in the same AE of special interest table. Hypoglycemia events by severity, and amputations will be summarized separately. Additional information will be collected for DKA. These data will be listed if available.

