9.3.3.4. Renal Failure Events

Frequency and percentage of subjects will be summarized for:

- Any acute kidney event;
- Acute kidney event by stage of disease. If a subject has multiple events, the highest stage will be summarized.

All instances of acute kidney event and their stage will be listed.

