laboratory reports so the sponsor, investigators, study coordinators, pharmacists, study subjects, and the CEC members will remain blinded to the dosing assignment.

The baseline value will be the latest value obtained on or prior to Day 1. Change from baseline for all continuous parameters will be calculated as the post-baseline value minus the baseline value.

Data summaries will use descriptive statistics (number of subjects [n], mean, standard deviation [SD], median, minimum and maximum) for continuous variables, and frequency and percentage of subjects for categorical and ordinal variables

Observed values (in SI units) and change from baseline over time will be summarized by treatment group. Laboratory data will be classified as low, normal, or high relative to the parameter's reference range. Laboratory abnormalities for each treatment will also be summarized with shift tables for selected parameters.

All laboratory data will be listed. For hematology, chemistry, including serum lipids, columns will be included for normal ranges and individual abnormal laboratory values will be flagged and clinical significance will be indicated. Listing for urinalysis will include the microscopic examination provided for subjects who have a positive result from the urinalysis dipstick evaluation.

Table 4 List of Laboratory Tests

Test Name	Blood or Urine Vol. (mL)	Shipment
Hematology	2 (blood)	Ambient
-Hematocrit (Hct)	-Mean corpuscular volume (MCV)	
-Hemoglobin (Hgb)	-Red cell distribution width (RDW)	
-Mean corpuscular hemoglobin (MCH)	-Red blood cell (RBC) count	
-Mean corpuscular hemoglobin concentration (MCHC)	-White blood cell (WBC) count with differential	
-Platelet count		
Serum Chemistry and Electrolytes	10 (serum)	Ambient
-Albumin (ALB)	-Calcium (Ca)	
-Alanine aminotransferase (ALT)	-Magnesium	
-Aspartate aminotransferase (AST)	-Phosphorus	
-Blood urea nitrogen (BUN)	-Potassium (K)	
-Glucose	-Sodium (Na)	
-Bicarbonate (HCO ₃)	-Total bilirubin	
-Creatinine	-Direct bilirubin	
-Chloride (Cl)	-Uric acid	
-Total protein		
Glycemic Control		Ambient
-Fasting plasma glucose (FPG)	2 (plasma)	
-Hemoglobin A1c (HbA1c)	2 (blood)	
Serum Lipids	6 (serum)	Ambient
-Total cholesterol (TC)	-Low-density lipoprotein cholesterol (LDL-C), calculated	
-High-density lipoprotein cholesterol (HDL-C)	-LDL-C, direct (if applicable)	
-Triglycerides (TG)		
Urinalysis	10 (urine)	Ambient
-Appearance	-Nitrite	
-Bilirubin	-Occult blood	
-Color	-pH	
-Glucose	-Protein	

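### Stage 1 creatinine rises that reverse by the recheck need not be adverse events, and the SAP does not say whether its staged kidney-injury count would pick them up

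*Protocol*

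**What the plan says.** **AE entry.** Protocol 3.2.5.1 deals with a creatinine increase that suggests possible stage 1 AKI. The investigator confirms it within 48 hours of learning the result and is to "enter an AE into the CRF if the serum creatinine does not spontaneously returns to < 0.3 mg/dL from baseline". Appendix 3 sets stage 1 at "1.5 to 1.9 times baseline or" a rise of at least 0.3 mg/dL.

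**Other AE text.** Protocol 6.16.14 refers back to 3.2.5.1 and asks for evaluation and documentation of "Events potentially representing renal failure events, including reversible and irreversible AKI, oliguria, and use of renal replacement therapy". Under protocol 6.16.2, a laboratory value "determined to be a clinically significant and abnormal change from baseline for that subject, this is considered a laboratory AE"; the investigator decides and may repeat the test first.

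**Special-interest row.** SAP 9.3.3 says that these events "will be prospectively identified based on the MedDRA PTs in the AEs log by a medical expert" before unblinding. Only MACE and amputations are excepted; renal failure events are not.

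**Staged count.** SAP 9.3.3.4 plans the number of subjects with any acute kidney event and "Acute kidney event by stage of disease. If a subject has multiple events, the highest stage will be summarized", with a listing of all events. The index gives this its own table (14.3.1.11), apart from the special-interest table (14.3.1.9).

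**Laboratory summaries.** SAP 9.4 plans change from baseline by treatment group. It adds that "Laboratory data will be classified as low, normal, or high relative to the" reference range of each parameter, with shift tables for selected parameters.

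**The concern.** The trial enrolls subjects with eGFR 30 to 59, and its safety objective is 24 weeks of exposure. Protocol 3.2.5.4 names renal failure events and diuretic effects, including hypovolemia, as events of special interest. Protocol 3.2.5.1 itself links a stage 1 rise to hydration advice. A creatinine rise that meets stage 1 and then reverses is therefore a signal that the renal safety section should be able to show by arm.

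Only one renal output has a stated source, the special-interest row, and it depends on AE entry that protocol 3.2.5.1 does not require for such rises. Protocol 6.16.14 names reversible AKI without saying whether a rise that reverses by the recheck belongs to it. Entry is then left to judgment under 6.16.2, which can differ between sites.

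**Working it through.** The plan states no figure on this point, so there is none to reproduce. The check sets the texts side by side and adds two small calculations.

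**1. What the AE rule leaves out**

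| Creatinine course | AE under protocol 3.2.5.1 | Special-interest row (SAP 9.3.3) | Staged count (SAP 9.3.3.4) |
|---|---|---|---|
| Possible stage 1, back within 0.3 mg/dL at recheck | Not required; allowed by judgment under 6.16.2 | Only if entered | Depends on unstated source |
| Possible stage 1, still raised at recheck, recovers later | Required | Can be picked up | Counted from either source |
| Possible stage 2 or 3 | The exemption is not written for these | As entered | As entered, or from the laboratory |

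The gap is the first row only.

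**2. Is the source of the staged count settled elsewhere?**

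- *Toward AE records:* the title of Table 14.3.1.11 calls the events treatment-emergent, a term that SAP 9.3 defines only for AEs. No AKI form is described, whereas hypoglycemia has a log (protocol 6.16.11), DKA a CRF (6.16.13) and amputation a form (6.16.15).
- *Toward another source:* AE severity is graded mild, moderate or severe (protocol 6.16.1), which is not an AKI stage. The AKI listings (16.2.7.2.13 and 16.2.7.3) are separate from the renal failure AE listing (16.2.7.2.11).

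The text does not decide it. Protocol Figure 1, the table shells and the SAS code are not in the public text.

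**3. Do the SAP 9.4 summaries fill the gap?**

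Change from baseline gives means, spread and extremes by visit, not the number of subjects crossing a threshold. SAP 6.4 keeps one record per visit window, the one nearest the target day, so an unscheduled peak can drop out. The SAP 9.4 prose also leaves week 6 out of the chemistry schedule, although SAP Table 1 and protocol Appendix 2 include it.

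The shift table helps only if creatinine is among the selected parameters, which is not stated, and only for subjects who start within range. The Appendix 4 equations give the eGFR at which creatinine equals an upper limit U:

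- General: eGFR = 175 × U^-1.154 × age^-0.203 (× 0.742 if female)
- Japanese: eGFR = 194 × U^-1.094 × age^-0.287 (× 0.739 if female)

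The documents give no reference range. Assume U = 1.3 mg/dL (men) or 1.0 (women), age 65, not African American, and eGFR evenly spread over 30 to 60:

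| Equation | Within range above eGFR | Share of 30–60 |
|---|---|---|
| General, men | 55.4 | (60 − 55.4)/30 = 15% |
| General, women | 55.6 | (60 − 55.6)/30 = 15% |
| Japanese, men | 43.9 | (60 − 43.9)/30 = 54% |
| Japanese, women | 43.3 | (60 − 43.3)/30 = 56% |

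With limits of 1.2–1.4 (men) and 0.9–1.2 (women), the general-equation shares at age 65 run from 0 to 30% and from 0 to 50%. For a subject who starts above range, a rise from 1.5 to 1.8 mg/dL changes no category.

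**4. How large is a 0.3 mg/dL rise?**

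From 1.5 to 1.8 mg/dL, eGFR is multiplied by (1.8/1.5)^-1.154 = 0.81, a 19% fall. The baseline b at which +0.3 mg/dL equals a 20% fall solves ((b + 0.3)/b)^-1.154 = 0.8, so b = 0.3/(0.8^(-1/1.154) − 1) = 0.3/0.2133 = 1.41 mg/dL. Above that baseline, the rise is a smaller change than the 20% that inclusion criterion 7 accepts as stable. The 1.5-times criterion is stricter: from 1.5 mg/dL it needs +0.75 mg/dL.

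**The case against.** The strongest reply is that protocol 3.2.5.1 describes a confirmation step, not a filter on reversible injury. It speaks of a possible stage 1 event and asks for the rise to be confirmed. Repeat testing before a laboratory AE is also the general option (6.16.2) and the liver-enzyme procedure (6.16.10). Protocol 6.16.14 points back to 3.2.5.1 and asks for documentation, not for an AE at every unconfirmed value, so the two can be read together. Step 4 supports this: many rises just over 0.3 mg/dL in this population may be ordinary variation. A separate staged count is planned as well, and it may already use laboratory values.

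Much of this stands. A recheck before AE entry is reasonable, and 6.16.2 keeps entry open. But a reasonable AE rule does not make AE records a complete count of threshold crossings, and the SAP does not say that the staged count uses anything else. Nor do the two protocol sections say whether a rise that reverses by the recheck is the reversible AKI to be documented.

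**Conclusion.** The point holds as a gap in specification, and closing it is a cheap improvement. The special-interest row can omit possible stage 1 rises that have spontaneously reversed at the recheck. Whether the staged count omits them too depends on a source that SAP 9.3.3.4 does not state. No output is stated to count subjects crossing an Appendix 3 threshold from laboratory creatinine.

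The size is unknown: the documents give no AKI rate and no reversal rate.

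Three stronger readings are tempting and not supported:

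- *That the renal safety count as a whole misses reversible injury.* Injury still present at the recheck that recovers later is entered, the exemption is not written for stage 2 or 3, and the staged count may be laboratory-based.
- *That every subject starts above the creatinine range, so a shift table can show nothing.* This rests on assumed limits. In step 3 it fits most of the eGFR range under the general equation but fails for over half of it under the Japanese one.
- *That the comparison between arms is pulled toward no difference.* This needs reversal to be more frequent on active drug. Equal reversal would lose events but keep the risk ratio, and the opposite pattern would inflate it. The documents support none of the three.

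**What to change.** In SAP 9.3.3.4:

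1. State the source, baseline and staging rule of the acute kidney event count already planned.
2. Add a derived table. For each subject, apply the Appendix 3 creatinine criteria to all post-baseline central-laboratory values, scheduled (including week 6) and unscheduled, against the central V3 value that protocol 6.11.1.3 names as baseline. Tabulate by arm and baseline eGFR group the subjects reaching each stage at any time, and whether the rise had resolved at the next value.
3. Within stage 1, show rises of at least 0.3 mg/dL alone separately from rises to at least 1.5 times baseline.
4. Show local-laboratory values separately if they are in the database. The documents do not say that they are, and they would be compared with a central baseline.
5. Keep the AE-based count beside the derived one. The low/normal/high shift table can stay.

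In the protocol, reconcile 3.2.5.1 with 6.16.14 so that both say whether self-reversing stage 1 rises are recorded. None of this touches dosing or the interruption of study drug.

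The cost is one table from creatinine already scheduled at V3, V5, V6, V8 and V9, plus unscheduled central values. The downside is that the row for at least 0.3 mg/dL alone will contain laboratory variation, most plainly above a baseline of about 1.41 mg/dL; this is why it is shown separately.

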3.2.5.2 Diabetic Ketoacidosis

DKA is a serious, acute complication of diabetes and can be life-threatening. Subjects will be educated on the signs and symptoms of DKA and are required to call the study clinic and seek treatment should such signs and symptoms occur.

During the clinical trial period, potential DKA will be monitored by the routine measurement of urinary ketones and assessment for signs or symptoms of acidosis at every clinic visit. Clinical presentations, such as difficulty breathing, abdominal pain, nausea, vomiting, lethargy, or a fruity smell in the breath, or laboratory values that suggest clinically-significant acidosis should be documented; treatment of DKA should be provided when appropriate.

If ongoing symptoms or signs suggest a possible DKA, the investigator should perform relevant laboratory testing while directing appropriate medical care for the subject. If DKA is suspected, regardless of the blood glucose level, the following assessments should be done immediately: physical exam and serum glucose, bicarbonate, electrolytes, and serum ketones

measured STAT at a local laboratory. If ketoacidosis is likely, investigational product administration should be discontinued and immediate appropriate medical therapy, including insulin, should be initiated. A glucose infusion may be provided if necessary to avoid hypoglycemia during insulin therapy. Insulin treatment should continue until resolution of the ketoacidosis and stabilization of the subject's clinical condition. Investigational product administration may be resumed following stabilization of the subject's condition. Investigator should collect the data necessary for the completion of the DKA CRF.

If symptoms suggestive of DKA may have occurred but are not ongoing, investigator should review available data in order to complete the DKA CRF. The investigator may also perform laboratory assessment using local resources if necessary for clinical care.

